## 9. QUALITY OF LIFE

### 9.1. CCI

CCI

A large rectangular area of the page is completely blacked out, indicating redacted content. The word 'CCI' is printed in red at the top left corner of this redacted area.

CCI

A smaller rectangular area of the page is completely blacked out, indicating redacted content. The word 'CCI' is printed in red at the top left corner of this redacted area.

Sponsor: Boston Pharmaceuticals, Inc.  
Protocol Number: BOS161721-02  
SAP Version and Date: Version 4.0, 23Apr2021

CCI

CCI

CCI

9.2. CCI

CCI

Sponsor: Boston Pharmaceuticals, Inc.  
Protocol Number: BOS161721-02  
SAP Version and Date: Version 4.0, 23Apr2021

CCI

CCI

CCI

CCI

CCI

CCI

## 10. SAFETY

All safety analysis reporting will be based on the Safety Analysis Set. Unless otherwise noted, all safety analyses will be presented overall, by study phase, and treatment group.

### 10.1. Adverse Events

AEs will be collected and recorded for each patient from the date of the first dose of study drug until the end of their participation in the study, including the safety follow up period. Severity of adverse events will be graded by the investigator according to National Cancer Institute Common Terminology Criteria for Adverse Events (NCI CTCAE) version 4.03. AEs will also be assessed for relationship to study drug, and seriousness. Adverse events will be marked as AESIs, dose-limiting toxicities (DLTs), or injection site reactions (ISRs), where applicable. AEs will be considered treatment-emergent adverse events (TEAEs) if they started any time after first dose or if the year, month and day of start date were missing. Any missing severity assessments will be assumed to be Grade 3, missing relationship assessments will be assumed to be related, and missing seriousness assessments will be assumed as serious.

An overview of TEAEs will be produced, including counts and percentages of patients with any incidences of TEAE, TEAEs related to study treatment, SAEs, SAEs related to study treatment, any CTCAE grade 2 or higher TEAEs, any CTCAE grade 2 or higher TEAEs related to study treatment, any CTCAE grade 3 TEAEs, any CTCAE grade 3 or higher TEAEs related to study treatment, any CTCAE grade 4 TEAEs, any CTCAE grade 4 or higher TEAEs related to study treatment, TEAEs leading to study treatment discontinuation, treatment related TEAEs leading to study treatment discontinuation, TEAEs of special interest, related TEAEs of special interest, DLTs, related DLTs, TEAEs resulting in death, related TEAEs resulting in death, and injection site reactions. The maximum CTCAE grade (Grades 1-5) will also be included on the summary table.

Adverse events will be coded based on the MedDRA. Patients will be counted once per SOC (and likewise for PT within SOC). TEAEs will be summarized by SOC and PT in descending order of overall incidence of SOC (and PT within SOC). The MedDRA version used is defined in the study data management plan.

Summaries of adverse events by SOC and PT will include the following types:

- TEAEs;
- TEAEs related to study treatment;
- SAEs;
- Related Serious TEAEs;
- CTCAE Grade 3 or higher TEAEs;
- CTCAE Grade 3 or higher TEAEs related to study treatment;
- TEAEs leading to treatment discontinuation; and
- Dose-Limiting Toxicities
- TEAEs of Special Interest

A summary of TEAEs by SOC, PT, and maximum CTCAE grade will also be prepared. For these summaries, TEAEs will be sorted for each patient by SOC/PT and CTCAE grade; patients will be counted once within a SOC/PT based on their maximum CTCAE grade. Missing CTCAE grade will be counted as grade 3 and will also be presented in a 'Missing' row for completeness.

A summary of TEAEs by PT and maximum CTCAE grade will also be prepared with sections for any TEAE and TEAEs related to study treatment. For these summaries, patients will be counted once within a PT based on their maximum CTCAE grade. Missing CTCAE grade will be counted as grade 3. An additional summary of TEAEs by PT and maximum CTCAE grade will be summarized for all TEAEs and TEAEs related to treatment for PTs with at least one patient experiencing a CTCAE grade 3 or higher and PTs where 10% or more of patients experience a CTCAE grade 1 or 2 for that PT. The summary will be sorted by the total incidence of the PT in the any TEAE section.

A comprehensive listing of all AEs will be provided in a by-patient data listing for the safety analysis set. In addition, the following listings will be provided for the safety analysis set:

- TEAEs related to study treatment;
- SAEs;
- TEAEs leading to treatment discontinuation; and
- AESIs
- CTCAE Grade 3 or Higher TEAEs

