|                                 | Treatment-Emergent | 
Scenario 1:
 
(1) Negative ADA at baseline
 
(2) Confirmed positive ADA at the post-baseline timepoint
 
Scenario 2:
 
(1) Confirmed positive ADA at baseline
  |   |

|         |          |  |  |
|---------|----------|--|--|
|         |          | (2) Confirmed positive ADA at the post-baseline timepoint and the titer at the of the confirmed positive ADA is $\geq 4$ times greater than the baseline titer |  |
|         | Negative | Negative ADA at the post-baseline timepoint  |  |
| Overall | Positive | A patient with positive baseline (pre-dose) ADA or positive post-baseline ADA  | Number of patients with a baseline or post-baseline ADA assessment |
|         | Negative | A patient with negative baseline (pre-dose) ADA and negative post-baseline ADA at all time points  |  |

The frequency and percentages of positive and negative neutralizing antibodies will be summarized in the FAS overall and at each relevant post-baseline timepoint (i.e., Day 15, Day 30, Day 60, Day 90, Day 180, Day 270). The denominators will be the number of patients with non-missing NAb data overall and at each timepoint, respectively.

The adverse event overview table from section 10.1 will be repeated by post-baseline positive and negative ADA as defined in table 7 in the safety analysis set. Additional adverse event analyses may be performed by post-baseline transient positive and persistent positive.

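### In the adverse-event overview, the all-cause Grade 3 and Grade 4 rows lack the 'or higher' threshold of their treatment-related partners, so a related count can exceed its all-cause count

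*SAP*

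**What the plan says.** SAP Section 10.1 defines the overview table by "counts and percentages of patients with any incidences of TEAE" and then by a list of row types, most of them paired as all-cause and treatment-related. The three graded pairs are:

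- Grade 2, both rows: "any CTCAE grade 2 or higher TEAEs, any CTCAE grade 2 or higher TEAEs related to study treatment"
- Grade 3, both rows, followed by the all-cause Grade 4 row: "any CTCAE grade 3 TEAEs, any CTCAE grade 3 or higher TEAEs related to study treatment, any CTCAE grade 4 TEAEs"
- Grade 4, related row: "any CTCAE grade 4 or higher TEAEs related to study treatment"

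The same paragraph adds: "The maximum CTCAE grade (Grades 1-5) will also be included on the summary table". The overview also has all-cause and related rows for TEAEs resulting in death. Further on, Section 10.1 plans summaries by system organ class (SOC) and preferred term (PT) of Grade 3 or higher TEAEs, both all-cause and related, as well as tables by maximum grade and a by-patient listing of Grade 3 or higher TEAEs.

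Section 8.3, in the text after Table 7, reuses the overview: "The adverse event overview table from section 10.1 will be repeated by post-baseline positive and negative ADA".

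**The concern.** A related row should be a subset of the all-cause row beside it. That holds for the Grade 2 pair, where both rows have the same threshold. In the Grade 3 and Grade 4 pairs the all-cause row names a single grade while the related row is cumulative, so the two are not nested and cannot be compared.

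Safety is the primary endpoint of the MAD part, and Section 2 names adverse events by severity and relatedness as an endpoint in both parts. These are the overview rows that cross the two. The active MAD arms have only 5 or 9 patients (Section 3.1.1), so one patient is visible in any row. The version by ADA status inherits the same definitions, and it is the only adverse-event table by ADA status to which Section 8.3 commits.

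Two imputation rules in Section 10.1 add to the mismatch. Missing severity is taken as Grade 3, so an ungraded event enters the all-cause Grade 3 row while a true Grade 4 or 5 does not. Missing relationship is taken as related, so a Grade 4 or 5 event of unknown causality enters the related Grade 3-or-higher row but not the all-cause Grade 3 row.

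**Working it through.** The plan states no figure to reproduce. The check counts patients under each row definition, first as written and then with matched thresholds.

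**Inputs.** Row definitions and counting unit: Section 10.1. Arm size for illustration: 9 active patients in MAD Cohort 2 or 3, Section 3.1.1. The event patterns are hypothetical, because the SAP contains no adverse-event data.

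**Definitions.** For k = 3, 4:
- all-cause as written: patients with any event of grade = k
- related as written: patients with any related event of grade ≥ k
- all-cause corrected: patients with any event of grade ≥ k

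**Cohort A** (n = 9): one patient with a related Grade 3, one with a related Grade 4, seven with an unrelated Grade 1.

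| Row | As written | Corrected |
|---|---|---|
| All-cause Grade 3 | 1/9 = 11.1% | 2/9 = 22.2% |
| Related Grade ≥3 | 2/9 = 22.2% | 2/9 = 22.2% |
| All-cause Grade 4 | 1/9 = 11.1% | 1/9 = 11.1% |
| Related Grade ≥4 | 1/9 = 11.1% | 1/9 = 11.1% |

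**Cohort B** (n = 9): one patient with an unrelated Grade 3, one with a related Grade 5, seven with an unrelated Grade 1.

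| Row | As written | Corrected |
|---|---|---|
| All-cause Grade 3 | 1/9 = 11.1% | 2/9 = 22.2% |
| Related Grade ≥3 | 1/9 = 11.1% | 1/9 = 11.1% |
| All-cause Grade 4 | 0/9 | 1/9 = 11.1% |
| Related Grade ≥4 | 1/9 = 11.1% | 1/9 = 11.1% |

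**All small profiles.** With five grades, each related or not, there are 10 event types. A patient with at most two distinct events has 1 + 10 + 45 = 56 possible profiles. A related row exceeds its all-cause row in these cases:
- single events: related Grade 4, related Grade 5: 2
- pairs with a related Grade 4 or 5 and no Grade 3: 28 − 15 = 13 (pairs among the 8 event types that are not Grade 3, less pairs among the 6 that are also neither related Grade 4 nor related Grade 5)
- a related Grade 5 together with a Grade 3, where the Grade 4 pair fails: 2

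The total is 2 + 13 + 2 = 17 of 56 as written, and 0 of 56 with both rows at ≥ k. This count shows which patterns break the nesting; it is not a probability.

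**Recovery from the same table.** Summing the maximum-grade rows 3 to 5 gives all-cause Grade ≥3. In cohort A this is 1 + 1 + 0 = 2, and in cohort B 1 + 0 + 1 = 2. Summing rows 4 and 5 gives Grade ≥4: 1 + 0 = 1 in A and 0 + 1 = 1 in B. All four match the corrected counts.

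**The case against.** A reader might infer that the plan understates severe toxicity at each dose. The SAP does not support that. Only two labelled rows can read low. The maximum-grade rows of the same table yield the all-cause totals, fatal events have their own rows, and Grade 3 or higher TEAEs are tabulated by SOC and PT and listed by patient. No severe event drops out of the report. The repeat by ADA status is a repeat of the whole table, so its maximum-grade rows go with it. No test, estimate or decision rule uses these rows, and Section 3.1.2 records that the phase 2 dose was selected on PK and PD data.

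It can also be said that the SAP never says *exactly* Grade 3. Given the Grade 2 pair and the SOC/PT summaries, two omitted words are the likelier explanation. The row labels may be right in the mock shells, which Section 13.12 keeps in a separate document that is not at hand. Nor would the overview necessarily disagree with the SOC/PT table: that needs the literal reading and at least one patient whose severe events are all Grade 4 or 5.

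All of this stands, and it limits the weight of the point. It does not make the row definitions right. Being able to rebuild a total from other rows does not correct a mislabelled pair, and a programmer who follows the text would produce rows that are not nested.

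**Conclusion.** The row definitions are inconsistent as written. Under the literal reading, the all-cause Grade 3 and Grade 4 rows can read low and a related count can exceed its all-cause count, in the main overview and in its repeat by ADA status. Each affected patient shifts a row by 1/9 = 11.1 percentage points in a 9-patient arm or 1/5 = 20 in the 5-patient arm; whether any such patient exists cannot be known from the SAP.

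This is a minor consistency error in a descriptive table. It affects no inference, and the claim that severe toxicity is understated does not follow from it. The conclusion assumes that the tables are programmed from the text of Section 10.1 and that the maximum-grade rows cover all TEAEs regardless of relationship.

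**What to change.** In Section 10.1, change the two all-cause rows to *any CTCAE grade 3 or higher TEAEs* and *any CTCAE grade 4 or higher TEAEs*. They then match the Grade 2 pair and their related partners, and the Grade 3 row also matches the SOC/PT summaries. Nothing is lost, because the maximum-grade rows still show each patient's highest single grade. Check that the mock shells carry the same labels, including the version by ADA status. The cost is two row labels in the SAP and, if needed, the shells; no data collection or analysis method changes.

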## 10.2. Clinical Laboratory Evaluations

Laboratory tests will be performed at times defined in the protocol Schedule of Assessments. Clinical chemistry and hematology parameters will be reported based on the International System of Units (SI). The following laboratory evaluations will be reported in data summaries, with asterisks indicating those that will be graded using NCI CTCAE. Grading will be performed by the Central Lab for relevant laboratory parameters based on the details provided in Appendix 13.11. If a grade is not present in the central lab database for a graded lab parameter, the grade will be analyzed as grade 0.

Hematology: Hemoglobin\*, Hematocrit, RBC count, RDW, MCV, MCH, MCHC, Platelet count\*, WBC count\*, CD4+ count\*, Total neutrophils (Abs)\*, Eosinophils (Abs), Monocytes (Abs), Basophils (Abs), Lymphocytes (Abs)\*

Clinical chemistry: Alanine Aminotransferase\*, Albumin\*, Alkaline Phosphatase\*, Aspartate Aminotransferase\*, Bicarbonate, Bilirubin\*, Blood urea nitrogen, C Reactive Protein, Calcium, Chloride, Creatine Kinase\*, Creatinine\*, Glucose (fasting)\*, Glucose (random)\*, Potassium\*, Protein, Sodium\*, Uric acid\*, eGFR (Cockcroft-Gault)\*, eGFR (MDRD)\*, Total cholesterol (fasting)\*, LDL-C (fasting), HDL-C (fasting), Triglycerides (fasting)\*, Gamma Glutamyl Transferase (GGT)\*. Per protocol, GGT is collected in cases of potential drug-induced liver injury.

Sponsor: Boston Pharmaceuticals, Inc.  
Protocol Number: BOS161721-02  
SAP Version and Date: Version 4.0, 23Apr2021

Coagulation: Prothrombin Intl. Normalized Ratio\*, Prothrombin Time

Urinalysis: pH, Glucose (qual), Protein (qual)\*, Blood (qual)\*, Ketones (qual), Nitrates (qual), Leukocyte esterase (qual), Urobilinogen (qual), Urine bilirubin (qual), Microscopy

Observed values, changes, and percentage changes from baseline for hematology, clinical chemistry, and coagulation laboratory evaluations will be summarized at each visit and most extreme change. Endpoint analyses will be based on changes from baseline assessments at Days 120 and 210.

The number and percent of patients with a CTCAE toxicity grade of 3 or higher will be tabulated by laboratory evaluation with defined CTCAE grading at each visit for hematology, clinical chemistry, coagulation, and urinalysis (protein only). Patients with missing values post-baseline will be excluded from the summary. The denominator for percentages will be the number of patients with a post-baseline assessment for the laboratory parameter in question at that visit.

Hematology, clinical chemistry, coagulation, and urinalysis (protein only) shift tables displaying the shift from baseline to the worst value of CTCAE grade will be presented based on the most extreme change as it relates to the relevant CTCAE definition. CTCAE relating to “high/hyper” conditions will depend on the maximum post-baseline value while CTCAE “low/hypo” will be reported based on the minimum post-baseline value. Separate shift tables will be prepared for parameters with bi-directional toxicity grading. Lab parameters which are optional, such as gamma glutamyl transferase, will not be included in the shift tables.

Hematology and clinical chemistry laboratory data which is not graded will also be summarized in shift tables of baseline to each visit based on range categories of low (below lower limit of normal [LLN]), normal, and high [above upper limit of normal [ULN]]).

Urinalysis laboratory data (excluding protein) will also be summarized in a shift table of baseline to each visit based on range categories of low (below lower limit of normal [LLN]), normal, abnormal, and high (above upper limit of normal [ULN]).

Selected hematology and clinical chemistry laboratory results will be plotted over time for treatment group for MAD phase 1b portion of the study in the safety analysis set. The mean and SD of the change from baseline for selected hematology and clinical chemistry laboratory results will be plotted over time for the POC Phase 2 portion of the study in the safety analysis set.

All laboratory parameters as well as a summary of central laboratory tests and chest x-ray will be provided in patient data listings for all randomized patients. By patient listings of clinical chemistry and hematology data will be presented in the safety analysis set for the DMC and interim analysis only.

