## 2. STUDY OBJECTIVES AND ENDPOINTS

### 2.1. Multiple Ascending Dose (MAD) Phase 1b Study

| Objectives   | Endpoints   |
|--|---|
| 
Primary
 

To assess safety, tolerability, and immunogenicity of repeat doses of BOS161721 (20, 60, and 120 mg) administered subcutaneously (SC) in adult patients with moderately to severely active SLE on limited background standard of care treatment, in order to estimate the optimal dose.

 | 
Safety Endpoints
 

Incidence and severity of adverse events (AEs) and serious adverse events (SAEs), related AEs, AEs leading to study drug discontinuation, AEs by severity and relatedness

Injection site reactions

Columbia Suicide Severity Rating Scale (C-SSRS)

12-lead electrocardiograms (ECGs) parameter results at each visit and change from baseline

Vital signs (blood pressure [BP], heart rate, and temperature) parameter results at each visit and change from baseline

Clinical laboratory results and change from baseline

Physical examinations changes from baseline

Anti-drug antibodies (ADAs)

Study drug exposure/compliance

 |

| Objectives  | Endpoints   |
|-------------|---|
| Secondary   | 
Pharmacokinetic (PK) Endpoints
 
 
• BOS161721 concentration by visit and time point
 
• Maximum observed concentration (<math>C_{max}</math>), first time to maximum concentration (<math>T_{max}</math>), area under the concentration-time curve (AUC), terminal half-life (<math>t_{1/2}</math>), systematic clearance (<math>Cl</math>), volume of distribution (<math>V_d</math>)
 
 
Pharmacodynamic (PD) Endpoints
 
 
• Results and changes (or shifts) from baseline to each visit in phosphorylated signal transducer and activator of transcription 3 (pSTAT3), C3 and C4 levels, and leukocyte immunophenotype
 
• Results and changes (or shifts) from baseline in anti-double-stranded DNA (dsDNA), antinuclear antibodies (ANA), anti-Sjögren syndrome A and B (SSA, SSB), Smith (Sm), and antiphospholipid (APL) autoantibodies at each visit
 
• Results and changes (or shifts) from baseline in abrogation of IL-21 gene signature at each indicated visit
 
 |
| Exploratory | 
 
• CCI
 
    |

Sponsor: Boston Pharmaceuticals, Inc

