| Triglycerides                    | 150 - 300                 | > 300 - 500              | > 500 - 1000              | > 1000   | mg/dL                         |
|                                  | 1.71 - 3.42               | > 3.42 - 5.70            | > 5.70 - 11.40            | > 11.40  | mmol/L                        |
| Troponin I                       | > 0.01 - < 0.30 (♀)       |                          | ≥ 0.30 (♀ & ♂)            |          | ng/mL or µg/L                 |
|                                  | > 0.03 - < 0.30 (♂)       |                          |                           |          | ng/mL or µg/L                 |
| Troponin T                       | > 0.01 - < 0.10           | -                        | ≥ 0.10                    | -        | ng/mL or mg/L                 |
| Uric acid                        | > ULN - 10.0  | -                        | > ULN - 10.0  | > 10.0   | mg/dL                         |
|                                  | > ULN - 590   | -                        | > ULN - 590   | > 590    | µmol/L                        |
| URINALYSIS                |                           |                          |                           |          |                               |
| Creatinine clearance             | 60 - < LLN                | 30 - 59                  | 15 - 29                   | < 15     | mL/min                        |
| Blood                            | + (++)                    | -                        | -                         | -        |                               |
| Protein                          | +                         | ++ or +++ (≥ 18y)        | -                         | -        |                               |
|                                  | < 1000                    | 1000 - 3499 (≥ 18y)      | ≥ 3500 (≥ 18y)            | -        | mg/24h                        |
| Protein/creatinine ratio (< 18y) |                           | 0.5 - 1.9                | > 1.9                     |          |                               |

Glucose: BARC reference range has no LLN, therefore 74 mg/dL (4.11 mmol/L) is applied as LLN in Grade I flagging (reference Tietz Clinical guide to laboratory tests 4th ed.)

Potassium: Grade II when intervention is indicated, else Grade I

Uric acid: Grade III, when in combination with physiologic consequences, else Grade I

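### The urine protein row of the Grade 3-or-higher laboratory table is zero by construction, because the only graded protein test listed stops at Grade II in adults

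*SAP*

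**What the plan says.** All references are to SAP Version 4.0.

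Section 10.2 sets out what is summarised and graded: "The following laboratory evaluations will be reported in data summaries, with asterisks indicating those that will be graded using NCI CTCAE". The urinalysis entry begins "Urinalysis: pH, Glucose (qual), Protein (qual"), and the protein item carries the asterisk. The list contains no 24-hour urine protein and no urine protein/creatinine ratio.

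The grades come from one source: "Grading will be performed by the Central Lab for relevant laboratory parameters based on the details provided in Appendix 13.11". If the central laboratory database holds no grade for a graded parameter, the SAP analyses it as Grade 0.

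The same section then plans a by-visit table: "The number and percent of patients with a CTCAE toxicity grade of 3 or higher will be tabulated", specifically "tabulated by laboratory evaluation with defined CTCAE grading at each visit for hematology, clinical chemistry, coagulation, and urinalysis (protein only"). It also plans a shift table from baseline to worst post-baseline grade, again with protein as the only urinalysis parameter.

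Appendix 13.11 has three urine protein entries: a +/++/+++ scale, a scale in mg/24h, and "Protein/creatinine ratio (< 18y"). Section 2.1 describes the population: "in adult patients with moderately to severely active SLE".

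**The concern.** A table of Grade 3 or higher is useful only for tests that can reach Grade 3. The urine protein row relies on a test whose adult scale ends one grade below the threshold, so its content is fixed before any data are collected. Nothing in the section warns of this.

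The disease gives the row weight. Proteinuria is a scored SLEDAI-2K item and BILAG has a renal domain, so a reader of the safety tables will look at urine protein. A line of zeros across dose levels and placebo invites the reading that nobody had severe proteinuria. The row carries no evidence either way.

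The shift table has a related limit. ++ and +++ share Grade II, so a patient who moves from one to the other shows no shift.

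**Working it through.** The SAP gives no figure for this point, so there is nothing to reproduce. The check is an enumeration.

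**Inputs.** The graded tests and the rule for an absent grade come from Section 10.2, the grade cut-offs from Appendix 13.11, and the adult population from Section 2.1.

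**Step 1: grade of each possible result for an adult on the listed test**

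| Qualitative result | Grade |
|---|---|
| No grade in the database | 0 |
| + | 1 |
| ++ | 2 |
| +++ | 2 |

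The maximum of {0, 1, 2, 2} is 2. The probability of Grade 3 or higher is therefore exactly 0, in every arm and at every visit, whatever the true level of proteinuria.

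**Step 2: other routes to Grade III in the appendix**

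- 24-hour protein: below 1000 mg is Grade I, 1000 to 3499 mg is Grade II (adults), and 3500 mg or more is Grade III (adults). This route could fill the row, but Section 10.2 does not list the test.
- Protein/creatinine ratio: the entry is restricted to patients under 18, so it does not apply.

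**Step 3: comparison with the rest of the table.** Each asterisked hematology, chemistry and coagulation test in Section 10.2 has a Grade III entry in the appendix. Urine blood is asterisked, can reach only Grade I, and is left out of the table. Urine protein is kept in, although its listed test cannot reach Grade III either. This looks like an oversight.

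**Step 4: what a row that could reach Grade III might show (illustration).** The documents give no prevalence of protein loss of 3500 mg/24h or more. I assume 2%, 5% or 10% at a visit, with every patient having a 24-hour result. The SAP does not show that such results exist. Approximate POC numbers are 110 × 2/3 ≈ 73 active and 110 × 1/3 ≈ 37 placebo. The expected count is n × p, and P(at least one) = 1 − (1 − p)^n.

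| Group | p = 2% | p = 5% | p = 10% |
|---|---|---|---|
| POC active (73), expected count | 1.5 | 3.7 | 7.3 |
| POC active (73), P(at least one) | 0.77 | 0.98 | >0.99 |
| POC placebo (37), P(at least one) | 0.53 | 0.85 | 0.98 |
| MAD 60 or 120 mg (9 active each), P(at least one) | 0.17 | 0.37 | 0.61 |
| MAD 20 mg (5 active), P(at least one) | 0.10 | 0.23 | 0.41 |
| Any group, listed qualitative test | 0 | 0 | 0 |

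In the small MAD cohorts a zero would often occur by chance anyway. In the POC groups a zero on a test able to reach Grade III would carry some information, whereas on the listed test it carries none.

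**The case against.** The strongest reply is that little is lost. The protein shift table, presented by phase and treatment group, still shows movement from Grade 0 or 1 to Grade 2. Investigators grade adverse events themselves, and TEAEs of Grade 3 or higher are tabulated and listed (Section 10.1). Creatinine and both eGFR measures sit in the same Grade 3-or-higher table and can reach Grades III and IV. SLEDAI-2K and BILAG carry renal items, BILAG flares are summarised by arm, and all laboratory parameters are listed by patient. All of this stands. A reader might infer that the plan hides renal harm, or any difference between doses or from placebo. The documents do not support that.

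A second reply is that Appendix 13.11 is the laboratory's general grading sheet. It covers tests outside this list, such as troponin and lipase, and some other rows also lack an upper grade. That is true, but INR, albumin and low hemoglobin lack only Grade IV. They can still reach Grade III, so their rows are not empty by construction.

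A third reply is that the table's wording names only protein, without the qualitative qualifier, and the appendix has a mg/24h row, so quantified results may be intended. The SAP alone cannot rule this out. If that is the intention, Section 10.2 needs to list the test.

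On display, a reader might expect 0% in these cells. Section 4 prints zero counts without a percentage, so the cell will show a bare 0. The risk of misreading is the same.

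**Conclusion.** The point holds for these laboratory displays. On the only graded urine protein test that Section 10.2 lists, the Grade 3-or-higher row is a structural zero in every arm at every visit and cannot be read as absence of severe proteinuria. The protein shift table cannot go above Grade II or separate ++ from +++.

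This rests on two readings: that the Section 10.2 list defines what is graded and reported, and that the +/++/+++ row of the appendix is the scale for the qualitative test. BILAG item 81 uses the same plus-sign scale for dipstick protein, which supports the second. No prevalence assumption is needed; the figures in the illustration only show scale.

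No efficacy endpoint or test is affected, and renal information remains in the other outputs. The correction is worth making because it is nearly free and the row as planned invites a false reading.

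**What to change.** For urine protein, tabulate Grade 2 or higher (++ or more) by visit and arm in place of Grade 3 or higher. Add a footnote to this table and to the shift table that the qualitative test cannot be graded above 2. The cost is one changed row and a footnote, using data the plan already reports. The downside is one row on a different threshold from the rest of the table, which the footnote explains.

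If the sponsor intends a quantified 24-hour protein to feed a Grade 3 row, Section 10.2 should list that test and take patients with that test at the visit as the denominator.

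I would not rely on the BILAG worksheet for this. Items 83 and 84 provide fields for a protein/creatinine ratio and a 24-hour protein, but nothing in the SAP shows that 24-hour collections were done, and item 84 shows no unit. Grading those values would also add a second route outside the central laboratory. If the test is done only on suspicion, the patients with a result would be a selected group.
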